## Adaptive tracking

The adaptive tracking test will be performed as originally described by Borland and Nicholson (Borland and Nicholson 1975) using customized equipment and software developed by Hobbs & Strutt.

The assessment includes a run-in time of 0.5 min, during which data are not recorded. Adaptive tracking is a pursuit-tracking task. A circle moves pseudo-randomly on a screen. The subject must try to keep a dot inside the moving circle by operating a joystick. If this effort is successful, the speed of the moving circle increases. Conversely, the velocity is reduced if the test subject cannot maintain the dot inside the circle. The average tracking performance (%) will be used as variable and recorded into the subject's eCRF.

The adaptive tracking test is more sensitive to impairment of eye-hand coordination by drugs than compensatory pursuit tasks or other pursuit tracking tasks, such as the pursuit rotor. The adaptive tracking test has proved to be useful for measurement of central nervous system effects of alcohol, various other psychoactive drugs, and sleep deprivation. The tracking performance test will take in total approximately 4 min.

## Body sway

The body sway meter allows measurement of body movements in a single plane, providing a measure of postural stability. Body sway is measured with a pot string meter (celesco) based on the Wright ataxiameter. At CHDR, the method has been used to demonstrate effects of sleep deprivation, alcohol, benzodiazepines and other psychoactive agents (data on file). With a string attached to the waist, all body movements over a period of time are integrated and expressed as mm sway. Subjects will be instructed to wear a pair of comfortable, low-heeled shoes on each session. Before starting a measurement, subjects will be asked to stand still and comfortable, with their feet approximately 10 cm part and their hands in a relaxed position alongside the body and eyes closed. Subjects may not talk during the measurement. The total period of body-sway measurement will be two minutes.

#### N-Back

The N-back test measures working memory. Following Rombouts et al., the N-Back test consists of three conditions, with increased working memory load: (Condition 0) "X" condition, in which participants are required to indicate whether the presented letter is a "X" (=target) or another letter; In Condition 1 and 2, letters will be presented sequentially (1.5 seconds for a letter [consonant, except for the letter "z"] presentation, followed by a black screen for 0.5 seconds). "z" is pressed on the keyboard for a target and "/" is pressed for a non-target. Condition 1, "1-back" condition, in which participants are required to indicate whether the letter presented is a repetition without any other letter intervening (e.g., B ... B); Condition 2, "2-back" condition, in which participants are required to indicate whether a letter is repeated with one other letter in between (e.g., B ... C ... B).The 3 conditions are presented in 3 blocks with increasing working memory load. Each condition starts with a training (7 consonants; ratio target : non-target 3:4), followed by the test (24 consonants; ratio target : non-target 1:3). This test takes approximately 10 minutes.

#### **Pupillometry**

The pupil size will be measured using the digital single-lens reflex camera Canon EOS 1100D. This procedure is performed on the NeuroCart®, which is equipped with Windows 7. To perform this measurement, a picture is taken from both eyes simultaneously. Consequently, the ratio between the pupil- and iris diameter are measured. In order to make sure that the measurement of the pupil size is independent of the distance between the camera and the subject, the ratios of the diameters are used.

During the measurement the subject will be seated in a chair while the subjects head is resting in a head support system. The measurements are taken in a room with lighting set at a marker. The marker is set for a certain amount of LUX, depending on the study protocol. Each measurement should be made under the same lighting conditions and with the subject's head in the same position.

The pupil measurements will be done with the help off the program Qpupil that has been designed by [name] (radiology department, LUMC, the Netherlands). This program has been designed to automatically calculate the ratio between the diameter of the iris and the pupil of both eyes.

### Visual analogue scales (Bond & Lader)

Visual analogue scales as originally described by Norris have often been used previously to quantify subjective effects of a variety of sedative agents . Dutch versions of the scales have been frequently employed at CHDR, for a variety of sedative agents and circumstances. A set of VAS assessing alertness, mood, and calmness (Bond and Lader) will be used for subjective assessment. The VAS allows the subjects to evaluate their current subjective states. The VAS Bond and Lader consists of 16 visual analogue scales, which allow the subjects to rate their subjective feelings and will be used to determine effects on alertness, mood, and calmness. Nine VAS items are combined to assess alertness, five VAS items are combined to assess mood, and two VAS items are combined to assess calmness. The algorithm to derive the variables is described in the SOP CGEVAS. Each VAS scale consists of a 100 mm horizontal line. Two words representing opposite feelings are placed to the left and right of the horizontal line. The subject is asked to mark his/her current feelings. The VAS will be scored from 0 to 100, with 0 reflecting the word placed to the left, e.g., alert and 100 reflecting the word placed to the right of the line, e.g., drowsy. It is important that the investigator checks for completeness to avoid omitted scales.

# Visual analogue scales (Bowdle)

Potential subjective psychotomimetic (psychedelic) effects of CNS-active agents can be evaluated using specific VAS. Bowdle Psychotomimetic Effects Scores have been used to quantify the psychotomimimetic effects of ketamine. No validated VAS is available for the Dutch language and population, but a translated version of the scales originally developed by Bowdle et al. has been used at CHDR to study CNS-active drug effects in multiple studies (data on file). Bowdle Psychotomimetic Effects Scores consist of thirteen 10 cm visual analogue lines ranging from 0 ('not at all) to 100 mm ('extremely'), addressing various abnormal states of mind.

#### Visual Verbal Learning Test (VVLT)

The Visual Verbal Learning Test (VVLT) contains three different subtests that cover merely the whole scope of learning behaviour (Schmitt et al 2001, De Haas *et al.* 2009). Subjects that perform the VVLT will be presented 30 words in three consecutive word trials, i.e. word learning test (VVLT30), according to CHDR's SOP CCNVVLT. Each trial ends with a free recall of the presented words (Immediate Recall- a test to determine acquisition and consolidation of information). Approximately thirty minutes after start of the first trial, the volunteers are asked to recall as many words as possible (Delayed Recall- this test measures active retrieval from long term memory). Immediately thereafter, the subjects will undergo memory recognition test, which consists of 15 presented words and 15 'distractors' (Delayed Recognition- testing memory storage). Importantly, subjects are not allowed to write words down at any time during the whole test procedure.

The VVLT scheduled at the 1-hour timepoint will test the "immediate recall, the "delayed recall and the VVLT at the 8-hour timepoint will assess the "delayed recognition".

## Pharmaco-electroencephalography

Pharmaco-Electroencephalography (pEEG) will be used to monitor any drug effects, which can be interpreted as evidence of penetration and activity in the brain. EEG provides non-specific measures of CNS functions. EEG recordings will be performed according to the guidelines of the International Pharmaco-EEG Society (IPEG).

## 2.10.4 Sequence of assessments and time windows

When the following assessments are scheduled to be performed at the same time-point, the order (of priority) will be as follows: ECG, vital signs, blood sampling for safety, NeuroCart® (pEEG (at applicable timepoints), Saccadic eye movement, Smooth pursuit eye movement, Pupillometry, Adaptive tracking, Bond & Lader, Bowdle, N-Back, VVLT, Body Sway, STAI), PainCart® (Heat pain (pre-cold pressor: unexposed/normal and Capsaicin-exposed skin) Pressure Pain test, Electrical Burst test, Electrical Stair test, heat pain test on unexposed/normal skin Cold pressor pain test, heat pain on unexposed/normal skin test), BSI and physical examination. When a PK assessment is scheduled for the same nominal time as another scheduled assessment, the blood sampling will take precedence.

The deviations of actual time points from the expected time points will be within ten percent, calculated from the zero point, time of drug administration. The expected timepoints are defined as the timepoints in Promasys. Deviations of more than 10% will be explained in a note. These time deviations only apply for ECG, vital signs, blood sampling for PK, first test of a NeuroCart® round, and first test of a PainCart® round.

Pre-dose assessments are given in indicative expected times.

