- Follow up (FU) visit after last treatment.
- Only weight will be measured at FU or upon early termination
- Physical examination at screening includes assessment of the Fitzpatrick skin type and evaluation of acne, freckles, tattoos or scarring on the back.
- A symptoms based physical examination will be performed.
- For women of childbearing potential: Urine beta HCG will be performed either during screening, on the first day of each treatment period or the day before the first day of each
- Treatment Period at discretion of Investigator. In either case, the results must be negative prior to dosing study participants.

  Vital signs will be measured in supine position. Oxygen saturation will be monitored after dosing at 2h until the end of study day 1 of each treatment period.
- Lunch at 0.5h and dinner 8h post dose, snack at 4.5h, time points are indicative. Light breakfast on Day 1 is shortly after wake activity around -3.5hours, after breakfast the subject starts fasting until after dosing. No meal restrictions on day -1 and day 2.
- PK sample taken 3 minutes after dosing
- Capsaicin application at screening must be performed on or before Day -5 to ensure sufficient washout between the capsaicin that is applied at screening and applied on Day 1.
- Capsaicin application will only be performed after enrolment in subjects not allergic or intolerable to the capsaicin solution, as determined at screening
- Sequence of assessments is NeuroCart® before PainCart®, for specific order of assessments see section 6.4.

  Capsaicin heat pain test (and heat pain test on control skin on volar forearm) will only be performed on subjects not allergic or intolerable to the capsaicin solution. Capsaicin heat pain task only applicable for Day 1.

  PainCart® training up to 42 days before dosing and NeuroCart® training up to 21 days before dosing.
- PainCart® and NeuroCart® will be done twice for baseline measurement
- NeuroCart® round with pEEG measurement only in second baseline measurement
- VVLT at 2u post dose will be measured is the immediate recall. VVLT at 5u post dose will be the delayed recall and recognition.
- Discharge time is approximate and only when deemed safe.

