#### Description and justification of dosage and route of administration

Study drug or placebo will be administered to the subjects as detailed in Table 1. Subjects will participate in four identical study periods. In each study period subject will receive a different drug combination, as described below. Two strengths of active (IV) morphine (see SmPC of morphine), 3 mg and 7 mg of morphine and 75 mg oral nortriptyline (see SmPC of nortriptyline), and matching placebo formulations will be manufactured. Each study participant will receive the following study treatments:

- Morphine 3 mg IV + 7 mg IV + placebo nortriptyline
- Nortriptyline 75 mg + morphine 3 mg IV + morphine 7 mg IV

Protocol time Treatments	0h00m	2h00m	5h00m
1	Placebo	Morphine 3 mg IV	Morphine 7 mg IV
2	Nortriptyline 75mg	Morphine 3 mg IV	Morphine 7 mg IV

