#### Morphine

Morphine and M6G notably contribute to the analgesic effect after administration of morphine, which is rapidly metabolized in the liver.26 As the study aims to have a better understanding of the analgesic effects of morphine and M6G in patients with chronic neuropathic pains and generate data that may be used for PK-PD modelling, an IV dose is deemed preferable over an oral dose.

Both morphine HCl 3 mg and 7 mg will be administered as intravenous bolus injection in 1 minute. In both the treatment arm with nortriptyline + morphine, and treatment arm with placebo + morphine, the bolus injections will be administered at t = 2 h (3 mg) and t = 5 h (7 mg).

The 3 mg and 7 mg doses of morphine are equianalgesic to minimally therapeutic and clearly therapeutic doses of buprenorphine as observed in a previous study where potentiation of buprenorphine and milnacipran was assessed.  Buprenorphine is 30-40 times more potent than IV morphine.  Testing two morphine doses, one minimally therapeutic and one clearly therapeutic, on a single study day will allow for detailed exploration of possible synergistic/potentiating effects of the combination treatment during the PKPD analysis. Furthermore, the 3 mg and 7 mg morphine doses are based on a calculation using pre-existing and published morphine and pregabalin  PK/PD models. Refer to Figure 1 for the predictions of effect of these doses on PTT for the cold pressor test. As illustrated in Figure 1, the proposed doses are predicted to yield an increased analgesic effect, while expected to have manageable side effects.

**Figure 1.** Predicted effect on cold pressor PTT based on the integrated PKPD model of morphine and pregabalin. Black line is the predicted placebo response, red line the proposed morphine dose of 3mg IV at t = 2 h and 7mg IV at t = 5 h, the green line the single oral dose of pregabalin 300mg at t = 0 and blue line the combination treatment of above-mentioned doses and drugs.

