### Analysis of pharmacokinetic endpoints

The individual plasma nortriptyline, morphine, and M6G concentrations will be listed by treatment, subject, visit and time. Individual plasma drug concentrations versus time will be plotted in panel plots for each treatment using both a linear and log y-axis.

The individual plasma morphine and nortriptyline concentrations will be summarised (number of samples [n], mean, standard deviation [SD], % coefficient of variation [CV], median, minimum [Min] and maximum [Max] values) by treatment and time, and will also be presented graphically as mean over time, with standard deviation as error bars.

When an actual sampling time of a drug concentration sample differs from the protocol time by more than 10% and at least 5 minutes, the concentration will be excluded from calculation of descriptive statistics and a note will be added to the sample in the listing. A sample will in general not be excluded from the non-compartmental analysis due to deviation from the protocol sampling times.

The individual PK parameters (except tmax and tlag) will be summarized (n, mean, SD, %CV, geometric mean, geometric %CV, median, Min and Max) per treatment group and will be presented graphically as boxplots. For tmax and tlag, the n, median, Min and Max statistics will be reported. The procedure for non-compartmental analysis at CHDR including the post and pre-processing of data is described in SOP SDANCA.

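### A 10% time window counted from the oral dose lets the morphine sample due 3 minutes after each bolus be drawn up to about 15 or 33 minutes after it and still count as on time

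*Protocol*

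**What the plan says.** - **Protocol, Section 2.10.4** sets one proportional rule: deviations "will be within ten percent, calculated from the zero point, time of drug administration". Its scope is stated: "These time deviations only apply for ECG, vital signs, blood sampling for PK", together with the first test of each NeuroCart and PainCart round. The consequence of exceeding it is mild: "Deviations of more than 10% will be explained in a note". Expected times are those held in the trial database.
- **Section 2.7.1** puts the oral dose (nortriptyline or placebo) at 0h00m, morphine 3 mg at 2h00m and morphine 7 mg at 5h00m. Each morphine dose "will be administered as intravenous bolus injection in 1 minute".
- **Table 1, footnote 9**, attached to the PK samples at 2 h and 5 h, reads "PK sample taken 3 minutes after dosing".
- **Section 2.13.6, Analysis of pharmacokinetic endpoints**, drops a concentration from the descriptive statistics only when its actual time "differs from the protocol time by more than 10% and at least 5 minutes". Such samples generally stay in the non-compartmental analysis.
- **Table 2** lists Cmax among the morphine PK parameters, under a secondary objective.

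**The concern.** A percentage of elapsed time is a sensible tolerance when there is one dose and concentrations change more slowly as time passes. Here there are three administrations on one clock, and the morphine profile restarts at 2 h and again at 5 h. The rule is therefore loosest where sampling needs to be tightest, and looser after the larger dose than after the smaller one.

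The 3-minute sample is the only one near each peak: in Table 1 the next PK samples are at 4 h (2 h after the first bolus) and 6 h (1 h after the second). If it is drawn late, no other sample recovers the peak. Because the exclusion rule uses the same 10%, the by-time means, SDs and plots would present such a value as a 3-minute concentration.

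**Working it through.** **Inputs.** Boluses at 120 and 300 min (Section 2.7.1). Samples due 3 min later, at 123 and 303 min (Table 1, footnote 9). Tolerance 10% of time since 0 h (Section 2.10.4). Morphine clearance 1.27 L/h/kg and volume of distribution 2.9 L/kg (Section 2.2.2). The protocol gives no figure of its own for these windows, so there is none to reproduce first.

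**Window = due time ± 0.10 × due time, then minus the bolus time.**

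| Sample | Due (min) | Tolerance (min) | Window on protocol clock (min) | Relative to bolus (min) |
|---|---|---|---|---|
| After 3 mg | 123 | ±12.3 | 110.7 to 135.3 | −9.3 to +15.3 |
| After 7 mg | 303 | ±30.3 | 272.7 to 333.3 | −27.3 to +33.3 |

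These are outer limits, one pair per bolus. If the database holds the samples at 2h00m and 5h00m, the windows become ±12 and ±30 min around the bolus, which changes little.

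**Exclusion rule.** A sample is dropped only if it is off by more than 10% and by at least 5 min. Since 12.3 and 30.3 min both exceed 5 min, the second condition does not tighten the first. The retained range is the one in the table.

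**Overlap with the next sample.** The 6 h sample is due at 360 min, ±36 min, so its window opens at 324 min. The 5h03m window closes at 333.3 min. Between 324 and 333.3 min a draw is on time under either label.

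**Size of the fall at the late edge.** One compartment, k = CL/V = 1.27/2.9 = 0.438 per hour. Relative to the concentration at 3 min:
- first sample, 12.3 min late: 1 − exp(−0.438 × 12.3/60) = 8.6%
- second sample, 30.3 min late: 1 − exp(−0.438 × 30.3/60) = 19.8%

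In this model the proportional fall does not depend on the dose, or on what remains of the 3 mg when the 7 mg is given. Section 2.2.2 notes that morphine has also been described with two or three compartments; a faster distribution phase would make the early fall larger.

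**The other reading of the zero point.** If it meant each bolus, 10% of 3 min is ±0.3 min (18 seconds), so the sample would be due between 2.7 and 3.3 min. The exclusion rule on that clock, now governed by its 5-minute condition, would keep draws from 3 − 5 = −2 min to 3 + 5 = +8 min around the bolus.

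**The case against.** **The zero point may mean each administration.** There are three a day, and footnote 9 uses dosing for the bolus. But Section 2.10.4 names a single zero point, and the protocol clock starts at the oral dose. The other reading gives 18 seconds after a 1-minute injection, which is hardly workable, and still leaves an exclusion rule that reaches 2 min before the bolus. The rule needs repair on either reading.

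**Footnote 9 governs the timing.** This stands for early draws. A reader might infer from the arithmetic that the protocol permits a 3-minute sample up to 9 or 27 min before the bolus. It does not: the footnote says after dosing, and a pre-bolus draw would contradict it. What remains is that neither the window nor the exclusion rule would flag such a draw. The footnote also sets no limit on lateness.

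**Other protections exist.** Section 2.10.4 gives PK sampling precedence over other assessments at the same time, which works against long delays. A separate laboratory manual (Section 2.10.3), not shown, may be stricter. Section 2.13.9 uses the scheduled time for PK parameters only when the actual time is missing, so the non-compartmental analysis evidently uses actual times. That protects AUC, but not a peak that was not sampled, nor the by-time summaries.

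**The pharmacodynamic consequences are easily overstated.** A reader might also infer that the 6 h PainCart round could start anywhere from 24 to 96 min after the 7 mg bolus (60 ± 36 min). The schedule makes that unlikely: NeuroCart rounds of about 40 min are set for 5 h and 6.5 h, so either extreme would collide with a neighbouring round unless that slipped too.

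**Conclusion.** The point holds for the two post-bolus morphine samples in each period. As written, draws up to 15.3 min after the 3 mg bolus and 33.3 min after the 7 mg bolus are on time and would be summarised as 3-minute values. At those extremes morphine concentration is about 8.6% and 20% below its 3-minute value. This assumes one compartment with the protocol's clearance and volume; the fall is larger if there is a faster distribution phase. These are permitted limits, and nothing in the protocol suggests that draws would cluster there.

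The effect is mainly on by-time morphine concentration summaries and Cmax, both secondary, in a study that calls itself exploratory. It would go too far to infer bias in the comparison of combination with morphine alone. Morphine doses, times and windows are the same in both treatments and the study is double-blind, so slippage has no evident reason to differ between them. AUC and any PK/PD model can use actual times. The point is worth correcting before the study starts because the rule is stated in the protocol itself and is cheap to change.

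**What to change.** - **Section 2.10.4:** state that windows for PK samples after a bolus are counted from that bolus. Give the two 3-minute samples a short absolute window, for example a minute or two, that opens only after the injection has ended.
- **Section 2.13.6:** for these two samples, replace the rule of 10% and at least 5 minutes by that same absolute window when deciding on exclusion from descriptive statistics. Moving the reference point alone is not enough, because the 5-minute condition would still keep draws from 2 min before to 8 min after the bolus. Keep actual times for the non-compartmental analysis.
- **Assessments scheduled at 2 h and 5 h** (NeuroCart and pEEG among them): state separately whether each comes before or after the bolus. Counting from the bolus does not settle this, and Section 2.13.6 admits to the ANCOVA only pharmacodynamic data collected after the start of the first bolus.

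The cost is wording in two sections and matching database checks, with a few more samples flagged as out of window.
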